4. STUDY DESIGN

4.1. Overall Design

This will be a Phase 2, Simon 2 stage minimax, open-label, single-arm study of neoadjuvant treatment of intratumoral tavo-EP plus nivolumab IV. Eligible subjects will be those with pathological diagnosis of operable locally-regionally advanced melanoma. The purpose and procedures of the study will be fully explained to potential subjects. Those wishing to enroll in the study will sign a written informed consent prior to initiating any study-related evaluations or procedures. Screening must be completed within 28 days prior to initiation of the study treatment (i.e. Cycle 1 Day 1; C1D1).

The Treatment period will be comprised of 3 phases:

Neoadjuvant Phase (Up to 3 x 4-week cycles, total 12 weeks): At every cycle, intratumoral tavo-EP will be administered (on Days 1 and 8) concurrently with 480 mg nivolumab IV infusion on Day 8 of each cycle (tavo-EP will be administered prior to nivolumab infusion).

Definitive Surgery Phase: Surgery may be scheduled about 2-4 weeks after the last dose of nivolumab following radiologic and clinical assessment at that point. Pathologic response will be determined by institutional pathologist. Refer to Appendix 8 (Section 10.8) for suggested guidelines on surgical management and techniques. These are important standard of care surgical guidelines and all investigators are strongly urged to consider them in the management of their patients. Under certain circumstances, the definitive surgery may be delayed and done after completion of additional cycles of neoadjuvant therapy if perceived by the treating physician investigators (surgeon and medical oncologist) to be in the best interest of the patient (or earlier if study intervention(s) was discontinued due to AEs or other reasons).

Adjuvant Phase: Adjuvant therapy with nivolumab monotherapy will begin approximately 2-4 weeks following definitive surgery; recovery from surgery is required (Day 1 of Cycle 4 will be determined by the treating investigator once the subject is cleared to initiate systemic therapy). Nivolumab (480 mg IV infusion on Day 1 of each 4-week cycle) will be administered for up to 9 cycles during the Adjuvant phase.

In Simon minimax Stage 1, up to 22 subjects can be enrolled. If the number of responders in Stage 1 meet the pre-specified number ($N \geq 3 // 22$), enrollment for Stage 2 will include an additional 11 subjects (for a total of 33 subjects).

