5.1. Inclusion Criteria

Subjects are eligible to be included in the study only if all of the following criteria apply:

Age

1. Subject must be ≥ 18 years of age inclusive, at the time of signing the informed consent.

Type of Subject and Disease Characteristics

2. Histologic diagnosis of melanoma belonging to the following American Joint Committee on Cancer (AJCC) 8th edition TNM stages (Tx or T1-4) and (N1b, N1c, N2b, N2c, N3b or N3c) and/or (M1a)
3. Must be considered surgically operable and may present as any of the following groups:
 - a. Primary melanoma with clinically apparent regional lymph node metastases, confirmed by pathological diagnosis.
 - b. Clinically detected recurrence of melanoma at regional lymph node basin(s), confirmed by pathological diagnosis.
 - c. Clinically or histologically detected primary melanoma involving multiple regional nodal groups, confirmed by pathological diagnosis.
 - d. Clinically detected single site of nodal metastatic melanoma arising from an unknown primary, confirmed by pathological diagnosis.
 - e. Subjects with in transit or satellite metastases with or without lymph node involvement are allowed if they are considered surgically resectable at Screening by the treating surgical oncologist.
 - f. Subjects with distant cutaneous/subcutaneous, soft tissue or nodal metastases with or without regional lymph node involvement are allowed if they are considered potentially surgically resectable and can be biopsied at Screening by the treating surgical oncologist. Elevated LDH is not an exclusion.
4. Subjects are eligible for this study either at presentation for primary melanoma with concurrent regional nodal and/or in-transit or distant metastasis, or at the time of clinically detected nodal, in transit, or distant recurrence.
5. Subjects must be evaluated by standard-of-care full body imaging studies including positron emission tomography – computed tomography (PET-CT ;preferred; including diagnostic CT component if possible) or CT (if PET-CT cannot be done) as well as magnetic resonance imaging (MRI) of the brain (or CT if MRI cannot be done) as part of the initial clinical work-up at Screening (no more than 4 weeks prior to Cycle 1, Day 1).
6. Have measurable disease based on RECIST v1.1, with at least one anatomically distinct lesion. Lesion or lesions must meet all the following baseline criteria:
 - a. Accessible for electroporation

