8.1.2. Response Evaluation Criteria in Solid Tumors (RECIST) v1.1 and immune RECIST (iRECIST)

Secondary efficacy endpoints will be evaluated using RECIST v1.1 ([Eisenhauer, 2009](#)) as described in Section [10.7.1 \(required\)](#) and iRECIST (optional), as described in Section [10.7.2](#).

Radiographic imaging will be assessed locally by the Investigator during the neoadjuvant phase (preoperative, unconfirmed); during the adjuvant phase, radiographic imaging and local assessments will be done only if feasible (as tumor is resected during surgery).

Disease staging will be collected at original diagnosis and at screening for this protocol, prior to any treatment initiation.

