9.4. Statistical Analyses

The statistical analysis plan (SAP) will be developed and finalized before database lock and will describe the subject populations to be included in the analyses, and procedures for accounting for missing, unused, and spurious data. This section is a summary of the planned statistical analyses of the primary and secondary endpoints. The SAP may modify the plans outlined in the protocol; however, any major modifications will also be reflected in a protocol amendment.

Since this is an open-label, single arm clinical study, descriptive summary statistics will be employed to analyze the data.

The standard summary statistics for continuous variables are sample size (n), mean, standard deviation, median, minimum and maximum. The standard summary statistics for categorical variables are frequencies and percentages. Time to event variables will be summarized using the Kaplan-Meier method. Where confidence limits are appropriate, the confidence level will be 95% (two-sided), unless otherwise stated. The only test of statistical significance will be performed according to the pre-defined analysis of the Simon 2-stage design.

Individual data (including relevant derived variables) will be presented by parameter in listings. Results of statistical analyses, descriptive summary statistics and supportive listings will also be presented.

Baseline values are defined as the last valid value prior to study drug administration. Baseline safety data will be presented along with subsequent safety values assessed during or after drug administration.

Statistical analyses will be performed using SAS® v9.4 or higher (SAS Institute, Cary NC, USA).

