9.4.3. Efficacy Analyses

Endpoint	Statistical Analysis Methods
Primary	
Primary efficacy analyses will be performed on ASaT Population.
 
The pCR will be estimated based on the proportion of subjects with no viable tumor on histologic assessment at definitive surgery. The estimated pCR will be accompanied by a 2-sided 95% exact binomial confidence interval (CI). Refer to statistical analysis plan (SAP) for detail.

Secondary	
DOR, PFS, iPFS, iBORR and OS (time to events endpoints) will be summarized descriptively using Kaplan-Meier methods. The censoring rules will be defined in the SAP. The ORR, BORR, and iBORR (categorical endpoints) will be summarized in a similar fashion as pCR. These will be assessed by Investigator based on Response Evaluation Criteria In Solid Tumors (RECIST) v1.1 at 12 weeks of Neoadjuvant phase (preoperative, unconfirmed). Refer to SAP for detail. Further, the risk of surgical delay (either due to toxicity and/or tumor progression) will be assessed. Surgery will be planned at about 12 weeks and any delays beyond the protocol allowed window will be monitored and reported.

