10.7.1.1. Evaluation of Overall Response with RECIST v1.1

The overall response recorded from the start of the treatment until disease progression/recurrence (taking as reference for progressive disease the smallest measurements recorded since the treatment started). The subject's best response assignment will depend on the achievement of both measurement and confirmation criteria ([Table 6](#)).

Table 6 Overall Response Definitions using RECIST v1.1

Target Lesions	Non-Target Lesions	New Lesions	Overall Response	Best Response for this Category Also Requires
CR	CR	No	CR	Normalization of tumor markers, tumor nodes <10 mm
CR	Non-CR/ Non-PD	No	PR	
CR	Not all evaluated	No	PR	
PR	Non-PD / No all evaluated	No	PR	
SD	Non-PD	No	SD	Documented at least once ≥ 4 weeks from baseline
Not all evaluated	Non-PD	No	NE	
PD	Any	Any	PD	
Any	PD*	Any	PD	
Any	Any	Yes	PD	

* In exceptional circumstances, unequivocal progression in non-target lesions may be accepted as disease progression

Source: ([Seymour, 2017](#))

Other definitions

- Duration of response (DOR)
- Relapse free survival (RFS) – RFS is defined as the time, in months, from the first dosing date until the date of disease relapse (i.e., the date of the tumor imaging) or death from any cause. RECIST v1.1 will be used to determine the dates of relapse as this methodology is accepted by regulatory authorities. This will be further detailed in the SAP.
- Overall survival (OS) - OS is defined as the time from diagnosis until death from any cause. Subjects without a confirmed date of death will be censored at the last date when the subject was known to be alive.

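### Overall survival starts at an undefined diagnosis date while RFS starts at first dose; if original diagnosis is meant, patients entering at recurrence bring guaranteed survival time and OS is inflated on average

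*Combined protocol and SAP*

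**What the plan says.** The definitions that close section 10.7.1.1 put two survival endpoints on different clocks. For overall survival, "OS is defined as the time from diagnosis until death from any cause"; patients with no confirmed death are censored when last known alive. For relapse-free survival, "RFS is defined as the time, in months, from the first dosing date until the date of disease relapse" or death.

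The word diagnosis can refer to more than one date in this trial:

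- Inclusion criterion 4 (section 5.1) admits patients at first presentation or "at the time of clinically detected nodal, in transit, or distant recurrence".
- Inclusion criterion 3b covers "Clinically detected recurrence of melanoma at regional lymph node basin(s), confirmed by pathological diagnosis", so a recurrence has a pathological diagnosis of its own.
- Section 4.1 uses the term for the qualifying disease: "Eligible subjects will be those with pathological diagnosis of operable locally-regionally advanced melanoma".
- Section 8.1.2 names the earlier date explicitly: "Disease staging will be collected at original diagnosis and at screening for this protocol".

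On analysis, section 9.4 says "Time to event variables will be summarized using the Kaplan-Meier method", and section 9.4.3 says "DOR, PFS, iPFS, iBORR and OS (time to events endpoints) will be summarized descriptively using Kaplan-Meier methods". Neither mentions delayed entry. Section 9.4.3 leaves censoring rules and further detail to the SAP. The synopsis counts survival follow-up from registration, which is a third reference date.

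**The concern.** A recurrent patient has at least two diagnosis dates, and section 10.7.1.1 does not choose between them.

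**Original melanoma diagnosis.** The interval from diagnosis to first dose is free of death by construction, because a patient must be alive to enrol. This is left truncation. Kaplan-Meier without delayed entry places these patients in the risk set from diagnosis, when they could not have been observed to die, and credits that time as survival. The resulting OS mixes time before the study with survival after the combined treatment.

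**Pathological confirmation of the current operable disease.** The gap to first dose may be only weeks and the distortion is small, but the clock still starts before enrolment and still differs from that of RFS.

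OS is a named secondary endpoint. With a single arm it can be interpreted only against outside series or beside RFS, and both uses need a known time origin. A confidence interval does not reveal a shift of this kind.

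**Working it through.** **Plan figures.** The documents state no survival assumption, event count or target for OS, so there is no OS figure to reproduce. The design figure does reproduce: an exact minimax search for 10% against 30% returns 22 then 33 patients, stopping at 2 or fewer responses in stage 1 and succeeding at 7 or more, with power 0.902 and attained type I error 0.041. None of this depends on how OS is timed.

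**One patient.** First dose 30 months after original diagnosis, death 6 months later. OS from original diagnosis = 30 + 6 = 36 months, so the patient counts as alive at 24 months. RFS is at most 6 months.

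**Assumptions for the group effect (none is in the documents).** A share *s* = 25% or 50% enters at recurrence, with gap *L* exponential with mean *m* = 12 or 36 months. Everyone else has a gap *U* uniform on 0-2 months. Survival from first dose is exponential with rate λ and independent of the gap.

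**Formula at 24 months.**

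S_dx(24) = s·E[S(max(24 − L, 0))] + (1 − s)·E[S(24 − U)]

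where, with k = 1/m − λ,

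- E[S(max(24 − L, 0))] = e^(−24λ)·(1 − e^(−24k))/(m·k) + e^(−24/m)
- E[S(24 − U)] = e^(−24λ)·(e^(2λ) − 1)/(2λ)

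**Worked case, true 80%.** λ = −ln(0.80)/24 = 0.00930 per month. Patients not at recurrence: 0.807. Recurrent patients: 0.883 for m = 12 and 0.944 for m = 36. For s = 0.25 and m = 12: 0.25 × 0.883 + 0.75 × 0.807 = 0.826.

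| True 24-month OS | s = 25%, m = 12 | s = 50%, m = 36 | Gap 0-2 months for all |
|---|---|---|---|
| 80% | 82.6% | 87.6% | 80.7% |
| 70% | 73.9% | 81.3% | 71.1% |

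The other two combinations for a true 80% give 84.2% (s = 25%, m = 36) and 84.5% (s = 50%, m = 12). At 36 months the same λ gives a true 0.80^1.5 = 71.6%, which reads about 74-81%. A Kaplan-Meier simulation with 400,000 patients per scenario agreed with the 24-month formula within 0.2 points.

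**At the trial's size.** 5,000 simulated trials of 33 patients per scenario; 24-month Kaplan-Meier from original diagnosis minus that from first dose:

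| Censoring after first dose | Mean shift, true 80% | Mean shift, true 70% | Trials where the diagnosis clock reads lower |
|---|---|---|---|
| 60 months | +2.6 to +7.7 points | +3.8 to +11.2 points | 0% |
| Uniform, 12-36 months | +2.7 to +8.1 points | +4.0 to +11.9 points | 1.0-17.2% |

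For scale, the 95% half-width without censoring is 1.96·√(p(1 − p)/33) = 13.6 points at 80% and 15.6 points at 70%.

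**Second set of assumptions.** Recurrent share 25-75%, mean gap 1-3 years (one month for the rest), true median OS 3 or 6 years, censoring at 5 years. Survival rose in every scenario, by about 3 to 20 points at 2 years. With a true median of 3 years, half the patients recurrent and a mean gap of 2 years, survival at 2, 3 and 5 years moved from 0.63, 0.50 and 0.31 to 0.75, 0.63 and 0.42, and the median from 3.0 to 4.1 years.

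**The case against.** The best case for leaving this alone is that it is an ambiguity, with a bias only under one reading, and that the harmless reading has textual support. Section 8.1.2 adds the word original when it means the first diagnosis, and section 10.7.1.1 does not. Section 10.8.2.4 speaks of diagnosing a nodal recurrence by baseline biopsy, and section 10.8 allows 4 weeks from baseline biopsy to first dose. On that reading the effect is about 1 point. Every input to the larger figures is assumed: with 10% entering at recurrence, a true 80% reads only 81.5-82.1%. Section 9.4 lets the SAP modify the protocol's plans, and the separate SAP is not available to check. OS is descriptive and untested. Registration, which already anchors survival follow-up, would serve as an origin as well as first dose does.

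Much of this is fair, and it limits the size of the claim. It does not supply an origin. Inclusion criterion 2 speaks only of a histologic diagnosis of melanoma, which fits either reading. The origin is stated in the protocol and is not among the items expressly deferred, so a SAP that followed the protocol would inherit the problem. Wide sampling error does not cancel a systematic shift. Registration would also remove nearly all of the pre-study interval; first dose has the advantage of matching RFS.

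**Conclusion.** The concern holds and should be fixed. OS has an undefined start that precedes enrolment on either reading and differs from the RFS start, and the planned Kaplan-Meier analysis makes no allowance for this.

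If original diagnosis is meant, 24-month OS is overstated by roughly 3 to 8 points at a true 80% and 4 to 11 points at a true 70%, given 25-50% recurrent entry, mean gaps of 12-36 months, and survival after first dose that is exponential and unrelated to the gap. A smaller recurrent share gives less; a larger share or longer gaps give more. The bias is upward on average, not in every data set: under staggered censoring some trials of 33 show a lower estimate from diagnosis. If confirmation of the current disease is meant, the shift is about 1 point and the remaining problem is reproducibility.

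Confidence is high that the origin is undefined and inconsistent with RFS. The size of the inflation is illustrative. The pCR decision, the sample size and the type I error are not affected.

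**What to change.** In section 10.7.1.1 and the SAP, define OS along these lines: *time in months from first dose of study intervention to death from any cause, in the ASaT population, with patients not known to have died censored at the date last known alive.* This puts OS and RFS on one clock.

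If survival from diagnosis is also wanted, state whether that is original diagnosis or confirmation of the current operable disease, and report it as a supplementary Kaplan-Meier curve with delayed entry at first dose and numbers at risk shown.

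The cost is small. First-dose dates are already needed for RFS, so no new data are required. All patients had completed the neoadjuvant phase by July 2023, so the change should be dated and disclosed as a late clarification. A change to the protocol text needs an amendment with IRB/IEC approval. Reported OS will be somewhat lower if original diagnosis had been intended, and a delayed-entry curve in at most 33 patients will be unstable early, when few are at risk.

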10.7.2. Immune-Related RECIST (iRECIST)

iRECIST will be used to assess a secondary endpoint (refer to [Section 3](#)) according to recently published consensus guidelines for iRECIST ([Seymour, 2017](#)).

Assessment by iRECIST will be done at 12-week intervals as specified in the SoA. Lesions will be numbered identically for each visit as Target and non-target, new lesions (see definitions in [Table 8](#)).

Immunotherapeutics may result in infiltration of immune cells leading to transient increase in the size in malignant lesions, or undetectable lesions becoming detectable. The criteria are identical to those of RECIST v1.1 in many respects but have been adapted to account for instances where an increase in tumor burden, or the appearance of new lesions, does not reflect true tumor progression.

Unlike RECIST v1.1, iRECIST requires the confirmation of progression and uses the terms iUPD (immune unconfirmed progression) and iCPD (immune confirmed progression).

For target lesions, iCR, iPR, and iSD can all be assigned after iUPD has been documented, if iCPD was not confirmed (Table 7). iUPD is defined by RECIST v1.1 criteria for progressive disease; iUPD can be assigned multiple times as long as iCPD is not confirmed at the next assessment. Progression is confirmed in the target lesion category if the next imaging assessment after iUPD (4–8 weeks later) confirms a further increase in sum of measures of target disease from iUPD, with an increase of at least 5 mm. However, the criteria for iCPD (after iUPD) are not considered to have been met if CR, PR, or SD criteria (compared with baseline and as defined by RECIST v1.1) are met at the next assessment after iUPD. The status is reset (unlike RECIST v1.1, in which any progression precludes later CR, PR, or SD). iCR, iPR, or iSD should then be assigned; and if no change is detected, then the timepoint response is iUPD.

The assessment of non-target lesions at each timepoint follows similar principles. iUPD (but not iCPD) can have been documented before iCR or when the criteria for neither CR nor PD have been met (referred to as non-iCPD/non-iUPD) and can be assigned several times, as long as iCPD was not confirmed. iUPD is defined by RECIST v1.1 criteria; however, iUPD can be assigned multiple times as long as iCPD is not confirmed at the next assessment. Progressive disease in the non-target lesion category is confirmed if subsequent imaging, done 4–8 weeks after iUPD, shows a further increase from iUPD. The criteria for iCPD are not judged to have been met if RECIST v1.1 criteria for complete response or non-iCR/non-iUPD are met after a previous iUPD. The status is reset (unlike RECIST v1.1) and iCR, or non-iCR/non-iUPD is assigned; if no change is detected, the timepoint response is iUPD.

iCPD is confirmed if further increase in tumor burden, compared to the last assessment, is seen as evidenced by one or more of the following:

- Continued increase in tumor burden (from iUPD) where RECIST v1.1 definitions of progression had been met (from nadir) in target, non-target disease or new lesions
 - Progression in target disease worsens with an increase of at least 5 mm in the absolute value of the sum
 - Continued unequivocal progression in non-target disease with an increase in tumor burden
 - Increase in size of previously identified new lesion (s) (an increase of at least 5 mm in the absolute value of the sum of those considered to be target new lesions) or additional new lesions.
- RECIST v1.1 criteria are met in lesions types (target or non-target or new lesions) where progression was not previously identified, including the appearance of additional new lesions.

If iUPD is not confirmed at the next assessment, then the appropriate response will be assigned (iUPD if the criteria are still met, but no worsening, or iSD, iPR or iCR if those criteria are met compared to baseline). The prior documentation of iUPD does not preclude assigning iCR, iPR, or iSD in subsequent time-point assessments or as immune best overall response (iBORR) providing that iCPD is not documented at the next assessment after iUPD.

The event date to be used for calculation of progression-free survival (iPFS) should be the first date at which progression criteria are met (i.e., the date of iUPD) provided that iCPD is confirmed at the next assessment. If iUPD occurs, but is disregarded because of later iSD, iPR, or iCR, that iUPD date should not be used as the progression event date

Table 7 iRECIST Time Point response

Target Lesions*	Non-Target Lesions*	New Lesions*	Time Point Response	
			No prior iUPD**	Prior iUPD**; ***
iCR	iCR	No	iCR	iCR
iCR	Non-iCR/Non-iUPD	No	iPR	iPR
iPR	Non-iCR/Non-iUPD	No	iPR	iPR
iSD	Non-iCR/Non-iUPD	No	iSD	iSD
iUPD with no change OR decrease from last time point	iUPD with no change OR decrease from last TP	Yes	NA	New lesions (NL) confirms iCPD if NLs were previously identified and increase in size (≥ 5 mm in sum of measure (SOM) for new lesion, target (NLT) or any increase for new lesion, non-target; NLNT) or number. If no change in NLs (size or number) from last time point, remains iUPD
iSD	iUPD	No	iUPD	Remains iUPD unless iCPD confirmed based in further increase in size of non-target disease (need not meet RECIST v1.1 criteria for unequivocal PD)
iUPD	Non-iCR/Non-iUPD	No	iUPD	Remains iUPD unless iCPD confirmed based on: 
 ○ further increase in SOM of at least 5 mm, otherwise remains iUPD
iUPD	iUPD	No	iUPD	Remains iUPD unless iCPD confirmed based on further increase in: 
 ○ previously identified T lesion iUPD sum of measure ≥ 5 mm and / or ○ NT lesion iUPD (prior assessment - need not be unequivocal PD)
iUPD	iUPD	Yes	iUPD	Remains iUPD unless iCPD confirmed based on further increase in: 
 ● previously identified Target lesion iUPD ≥ 5 mm and / or ● previously identified non-target lesion iUPD (need not be unequivocal) and /or ● size or number of new lesions previously identified
Non-iUPD/PD	Non-iUPD/PD	Yes	iUPD	Remains iUPD unless iCPD confirmed based on

				○ increase in size or number of new lesions previously identified
--	--	--	--	---

TP = time-point; NT = non-target, T = target; NL = new lesions; iUPD = unconfirmed immune PD; iCPD = confirmed immune PD; SOM = sum of measures. iCR – immune complete response; iPR – immune partial response; iSD – immune stable disease

* Using RECIST v1.1 principles. If no PSPD occurs, RECIST v1.1 and iRECIST categories for CR, PR and SD would be the same.

** in any lesion category.

*** previously identified in assessment immediately prior to this time point.

Source: [\(Seymour, 2017\)](#)

